##### 5.4.1. Adverse Events

Adverse event study periods will be classified as follows:

Event Type	Reporting Period	Additional Requirements
Adverse Events/Serious Adverse Events (Screening)	Date of informed consent and prior to first dose of study drug	Report as AE/SAE only if related to study procedures during Screening
Adverse Events (treatment-emergent)	First dose of study drug through 28 days following last dose of study drug	
Serious Adverse Events (treatment-emergent)	First dose of study drug through 90 days following last dose of study drug, or 28 days following last dose of study drug if the subject initiates new anti-cancer therapy	Report new SAEs outside of window if assessed as possibly or probably related to study drug
Event of Special Interest (treatment-emergent)	First dose of study drug through EOT visit	

Pregnancy of subject or partner	Date of informed consent through 28 days following last dose of study drug	Follow pregnancy reporting and follow-up procedures in Section 8.4 of the study protocol
---------------------------------	--	--

## 5.5. Baseline, Post-Baseline Changes, and Last Observed Value (LOV)

Unless stated otherwise, baseline and post-baseline change values will be based on the following:

Baseline will be based on the last non-missing value collected prior to or on the treatment start date [and time, if applicable]. Post-baseline values will be those collected after the treatment start date.

Change from baseline is defined as: value at visit – baseline value.

Percentage change from baseline is defined as: (value at visit – baseline value)/baseline value X 100%.

Most extreme change: The maximum most extreme change will be based on be the maximum grade change. This calculation will consider assessments collected during the on-therapy period and assessed with CTCAE grading, scheduled or unscheduled.

Maximum percent reduction is defined as the largest percent reduction in the change from baseline at any visit.

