- ⁶ Skeletal Survey: Radiographic imaging (includes standard radiography of cervical, thoracic and lumbar spine, skull, chest, pelvis, humeri and femora) conducted within 30 days prior to Screening may be used, otherwise collect prior to Cycle 1 Day 1; perform Screening MRI as follow-up only if X-ray survey appears normal in the setting of bone pain or neurologic deficits, or if the subject has a history of plasmacytoma of the bone. Additional imaging during the study may be performed at the Investigator's discretion, e.g. in case of bone pain.
- ⁷ SPEP/UPEP/IFE/FLC: Serum and urine monoclonal protein profiles including total protein and immunoglobulin (IgA, IgG and IgM) levels. Fasting is preferred for blood samples, but not required. Obtain 24-hour urine and blood samples on the same day if feasible, but not more than 7 days apart; 24-hour urine collection must be completed prior to dosing. Not required on Cycle 1 Day 1 if Screening assessment completed within 72 hours of dose administration. UPEP (24-hour urine sample): urine protein IFE and total protein measured at screening and Cycle 1 Day 1 (all subjects) and Day 1 of every Cycle thereafter only if Cycle 1 Day 1 UPEP ≥ 200 mg/24 hours; UPEP will also be collected (all subjects) to confirm a response or progression. Analysis of urine and serum samples will be performed at the institution's local laboratory; additional serum samples will be collected and stored to be evaluated at a central laboratory at a later date.
- ⁸ Vital Signs: Blood pressure, pulse, respiratory rate, and temperature. On dosing days, collect prior to dosing (-5 min) and at least every 30 minutes (± 5 min) during and after the infusion through the observation period until subject is considered clinically stable; perform additional monitoring as clinically indicated.
- ⁹ Physical Examination: Complete physical examinations at Screening and EOT; all other indicated visits are symptom-directed physical examinations. Not required at Cycle 1 Day 1 if Screening exam completed within 72 hours prior to Cycle 1 Day 1 visit. Weight at each indicated visit. Assessment may be done up to 3 days prior to visit.

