7.3.1 Inclusion Criteria

Individuals eligible to participate in this study must meet all of the following criteria:

1. Male or female, aged ≥ 18 years
2. Confirmed diagnosis of MM per IMWG criteria
3. Measurable disease as defined by one or more of the following:
 - Serum M-protein ≥ 0.5 g/dL
 - Urine M-protein ≥ 200 mg/24 hours
 - Serum Free Light Chain (FLC) assay: involved FLC level ≥ 10 mg/dL provided serum FLC ratio is abnormal
 - In cases where SPEP is unreliable, serum quantitative immunoglobulin (qIgA) ≥ 750 mg/dL (0.75 g/dL) is acceptable
4. Relapsed or refractory (Rajkumar et al. 2011) to 3 or more different prior lines of therapy for MM, including IMiDs, PIs, chemotherapies, or monoclonal antibodies, and not a candidate for, or intolerant to established therapy known to provide clinical benefit:
 - Relapse defined as progression of disease after an initial response (MR or better) to previous treatment, more than 60 days after cessation of treatment
 - Refractory disease defined as $< 25\%$ reduction in M-protein or progression of disease during treatment or within 60 days after cessation of treatment
5. Eastern Cooperative Oncology Group (ECOG) Performance Status of 0 – 1

6. Adequate organ and marrow function (i.e. without growth factors or transfusions) at Screening, as defined by the following laboratory parameters:

Hematologic	Renal	Hepatic
ANC \geq 1000/ μ L Platelets \geq 75,000/ μ L Hemoglobin \geq 7.5 g/dL Albumin \geq 3.0 g/dL	Creatinine clearance or eGFR >30 mL/min	AST/ALT \leq 3 \times ULN ALP \leq 2 \times ULN (ALP \leq 5 \times ULN for subjects with isozymes specific to bone) Bilirubin < 2 \times ULN; or Bilirubin \leq 3 \times ULN if due to Gilbert's disease ¹

¹ If diagnosis of Gilbert's disease has not been previously established, the following will be required: (a) evidence of prior isolated rises in bilirubin; (b) evidence that hyperbilirubinemia is due to rise in unconjugated bilirubin (indirect bilirubin); (c) normal CBC in previous 12 months; (d) blood smear and reticulocyte count; (e) evidence of normal transaminases and ALP in previous 12 months. ALP = alkaline phosphatase; ALT = alanine aminotransferase; ANC = absolute neutrophil count; AST = aspartate aminotransferase; eGFR = estimated glomerular filtration rate (Cockcroft-Gault); ULN = institutional upper limit of normal
		

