7.5.2.1.2 Urine Profiles

The subject will collect urine for a 24-hour period during Screening, and prior to dosing at Cycle 1 Day 1. The Cycle 1 Day 1 collection is not required if the Screening assessment was completed within 72 hours of Cycle 1 Day 1 dose administration. Additional 24-hour urine samples will only be collected on Day 1 of every Cycle thereafter if Cycle 1 Day 1 UPEP >200 mg/24 hours, or to confirm a response or disease progression. Urine will be tested at the institution's local laboratory.

Urine protein electrophoresis (UPEP) includes:

- urine IFE (IgG, IgA, IgM)
- total protein

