## 7.2. Urine and Serum M-Protein

Efficacy laboratory assessments were collected throughout the study. Change from baseline and percent change from baseline will be derived as applicable and displayed in subject listings. The maximum percent reduction from baseline will be summarized by cohort.

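### SAP 5.5 and 7.2 set no minimum baseline for the maximum percent M-protein reduction, so any subject with a low baseline on that analyte would be pooled with subjects who are measurable on it

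*SAP*

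**What the plan says.** SAP 5.5 gives the formula: "Percentage change from baseline is defined as: (value at visit – baseline value)/baseline value X 100" percent. It then defines the endpoint: "Maximum percent reduction is defined as the largest percent reduction in the change from baseline at any visit". SAP 7.2 adds: "The maximum percent reduction from baseline will be summarized by cohort". SAP 6.1 bases all reporting on everyone who received study drug, and SAP 4.2 plans no subgroups. The only qualifier in SAP 7.2 is that changes are derived as applicable. That phrase belongs to the sentence on listings and names no exclusion.

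Protocol 7.3.1 requires: "Measurable disease as defined by one or more of the following". The routes are serum M-protein of at least 0.5 g/dL, urine M-protein of at least 200 mg/24 h, involved free light chain (FLC) of at least 10 mg/dL with an abnormal ratio, or qIgA of at least 750 mg/dL where SPEP is unreliable.

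For urine, Protocol 7.5.2.1.2 limits routine collection: "Additional 24-hour urine samples will only be collected on Day 1 of every Cycle thereafter if Cycle 1 Day 1 UPEP" exceeds 200 mg/24 h (Table 2-1, footnote 7, has at or above 200). Footnote 7 also says: "UPEP will also be collected (all subjects) to confirm a response or progression". Serum M-protein is scheduled on Day 1 of each cycle with no such threshold.

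**The concern.** A percentage of a small number is unstable. A subject who enters on urine, FLC or qIgA may have a serum M-protein well below 0.5 g/dL, where ordinary assay variation is a large fraction of the baseline. Taking the largest fall over several visits then picks out the most favourable error.

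The protocol recognises the problem elsewhere. For partial response and progression, Appendix A replaces the M-protein criteria when serum and urine M-protein are not measurable. The SAP does not carry that distinction into this endpoint.

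Tumour response is only listed (SAP 7.1), so this is the one efficacy quantity that the SAP summarises. With 21 subjects in 6 cohorts (21/6 = 3.5 on average), one such subject can set a cohort's maximum and shift its mean, and SAP 4 reports both.

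**Working it through.** The plan gives no figure for M-protein reduction, so there is nothing to reproduce.

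**Inputs.** From the documents: the SAP 5.5 formula, the thresholds in Protocol 7.3.1, and 21 subjects in 6 cohorts (SAP 3.1). Assumed, because the documents give none of them: additive normal assay error with SD 0.025, 0.05 or 0.1 g/dL on baseline and on each visit; no true change; 2 or 6 post-baseline visits; visit values floored at 0; baseline above 0.

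**Step 1: the formula alone.** The same 0.1 g/dL fall gives 0.1/0.2 = 50%, 0.1/0.5 = 20% and 0.1/2.0 = 5%.

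**Step 2: noise at a single visit.** Let the true level be b, the baseline b + e0 and the visit b + e. A fall of at least 50% requires e − e0/2 ≤ −b/2. The left side has SD σ√1.25. With σ = 0.05:
- b = 0.2: z = −0.1/0.0559 = −1.79, probability about 3.7%.
- b = 0.5: z = −0.25/0.0559 = −4.47, probability effectively 0.

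**Step 3: the largest fall over 2 and over 6 visits** (simulation, 1,000,000 subjects per setting):

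| SD (g/dL) | Fall | True 0.2 g/dL | True 0.5 g/dL |
|---|---|---|---|
| 0.025 | ≥50% | 0.0–0.1% | 0% |
| 0.025 | ≥25% | 10–23% | about 0% |
| 0.05 | ≥50% | 7–18% | 0% |
| 0.05 | ≥25% | 34–60% | 4–11% |
| 0.1 | ≥50% | 33–63% | 2–7% |

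The two-visit figure of 7.1% at SD 0.05 and 0.2 g/dL agrees with roughly twice the single-visit 3.7%.

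**Step 4: effect on a cohort** (SD 0.05, 400,000 cohorts). Two flat subjects at 2.0 g/dL, without and then with one flat subject at 0.2 g/dL. Entries are the median over simulated cohorts of each statistic of the maximum percent reduction:

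| Cohort statistic | 2 visits | 6 visits |
|---|---|---|
| Mean | 1.4% to 5.5% | 3.1% to 12.5% |
| Maximum | 3.1% to 14% | 4.7% to 31% |
| Median | 1.4% to 2.0% | 3.1% to 4.3% |

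**Step 5: what a floor does near the cut.** For a true level of 0.5 g/dL, keeping only observed baselines of at least 0.5 selects baselines that read high by chance. The probability of a 25% fall rises from 4–11% to 8–20% (SD 0.05) and from 27–50% to 45–78% (SD 0.1).

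**The case against.** **The SAP follows the protocol.** Protocol section 6 defines the endpoint with no floor, and SAP 5.5 and 7.2 implement it as written. That is true, but Protocol 7.6 leaves the detailed method for each variable to the SAP, so the SAP is the place to settle it.

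**No affected subject is shown.** This stands. A reader might infer that the cohort summaries are in fact distorted, but the documents report no baseline values. A zero baseline gives no percentage at all, so only low non-zero values matter.

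**Urine is largely protected by the collection rule.** This stands in part. Subjects below about 200 mg/24 h have no routine on-study urine, but they are still sampled to confirm response or progression. Serum has no equivalent.

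**SAP 10 omits all efficacy analyses.** That phrase is attached to the Phase 2 objectives and endpoints. SAP 2 keeps M-protein reduction as a Phase 1 endpoint, and SAP 7.2 specifically plans the summary.

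**The harm is small.** This stands. There are no significance tests, the median barely moves, every percent change is listed, and Phase 2 was never enrolled. At SD 0.025 the 50% artefact almost vanishes.

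**A stronger reading.** A reader might also infer that taking the largest fall at any visit improperly admits values after treatment. The documents do not support this. The on-treatment limit is stated in Protocol 7.6.5.1 under a Phase 2 heading, and the Phase 1 endpoint has no such limit. SAP 5.7 bases summaries on nominal visits. Its allowance for unscheduled data in most-extreme summaries is most naturally read as the CTCAE-grade summaries that SAP 5.5 defines under that name.

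**Conclusion.** The concern holds as a minor weakness of method. The SAP has no rule to keep subjects with a low baseline on an analyte out of that analyte's cohort summary, and the eligibility criteria permit such subjects. The exposure is mainly in serum.

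If such a subject exists, assay noise alone could produce a 50% fall in anywhere from almost none to 63% of cases at 0.2 g/dL, against 0–7% at 0.5 g/dL. The width of that range reflects the assumed SD and number of visits. The baselines of 0.2, 0.5 and 2.0 g/dL are also chosen for illustration. The consequence is confined to descriptive means and maxima; no test or error rate is affected.

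**What to change.** In SAP 7.2, summarise serum only for subjects whose SAP 5.5 baseline is at least 0.5 g/dL, and urine only for those whose baseline is at least 200 mg/24 h. Both are the protocol's own entry thresholds. Show N per cohort. List all other subjects with their baseline values, flagged as not measurable on that analyte. Add a footnote that a maximum over visits is biased upward even with no true change.

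Apply the cut to the baseline itself. Cutting on the Screening value would avoid the selection effect in step 5. But where Cycle 1 Day 1 supplies a separate baseline, about half of subjects truly at 0.5 g/dL would be kept with a denominator below the threshold. It would also conflict with the urine collection rule, which is keyed to Cycle 1 Day 1.

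The work is a wording change and one filter. The costs are:
- N falls in cohorts that average 3.5 subjects, and some urine cells may be empty.
- Regression to the mean remains just above the cut, by the amounts in step 5.
- A qIgA-entry subject whose unreliable SPEP reads 0.5 g/dL or more is not caught.
- The upward bias of a maximum is disclosed, not removed.

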6 STUDY OBJECTIVES AND ENDPOINTS

The objectives of the study are to:

- Evaluate safety and tolerability of BION-1301 when administered as a single-agent or with low-dose dexamethasone (BION-1301+DEX)
- Identify the recommended Phase 2 dose (RP2D) and schedule of BION-1301 when administered as a single-agent
- Characterize the PK and PD profile of BION-1301
- Evaluate clinical activity of BION-1301 and BION-1301+DEX

The study has been designed with an appropriate study population, sufficient size, and duration to enable a preliminary assessment of safety and efficacy as related to the following specific endpoints:

ENDPOINTS:

Phase 1

- Incidence of DLTs, TEAEs, and changes in safety parameters
- PK parameters based on BION-1301 serum levels following a single dose and after repeated dosing
- Changes from baseline in soluble APRIL
- Relative reduction in serum and urine M-protein levels defined as the maximum percent reduction from baseline

Phase 2

- Objective response rate (ORR) based on International Myeloma Working Group (IMWG) uniform response criteria of stringent complete response (sCR), complete response (CR), very good partial response (VGPR), or partial response (PR)
- Relative reduction in serum and urine M-protein levels defined as the maximum percent reduction from baseline
- PFS defined as time from first dose of study drug to date of first tumor progression or death due to any cause
- OS defined as the time from first dose of study drug to date of death due to any cause
- Incidence of TEAEs, changes in safety parameters, and unacceptable toxicities
- PK parameters based on BION-1301 serum levels following a single dose and after repeated dosing

Exploratory Endpoints evaluated throughout the study as appropriate include:

- Duration of response (DOR) defined as the time from the first tumor assessment that supports the subject's ORR to the time of disease progression or death due to any cause
- Disease control rate (DCR) defined as the percentage of subjects with sCR, CR, VGPR, PR, or stable disease (SD) per IMWG criteria; or minimal response (MR) per European Group for Blood and Marrow Transplantation (EBMT) criteria.
- Change from baseline in soluble B cell maturation antigen (sBCMA; TNFRSF17) levels
- Changes in additional biomarkers and immune monitoring

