7.5 Study Assessments and Procedures

Screening assessments will be conducted to confirm eligibility and to obtain baseline measurements. Screening must be completed within 28 days prior to first dose of study drug. An enrollment form will confirm subject eligibility after completion of all screening procedures. Subjects must initiate dosing of study drug within 2 weeks from the date of the approved enrollment form.

Subjects will be requested to complete multiple clinic visits during the initial two dosing cycles; visit frequency is reduced beginning at Cycle 3 and beyond. An EOT Visit will occur 28 days after the last dose of study drug. If the subject begins another anticancer therapy before the end of the 28-day period, all EOT Visit assessments should be completed prior to commencing the new therapy. Unresolved AEs will be monitored until resolution or confirmed stability of the event.

Subjects who discontinue study treatment for reasons other than progressive disease should continue tumor response assessments as per the standard of care frequency until disease progression is documented, withdrawal of consent, or study end.

Follow-up calls will occur every 12 weeks after the last dose of study drug. Data will be collected on survival and any subsequent cancer-related therapies. Telephone contact(s) should also be scheduled to satisfy safety reporting requirements as specified in [Table 7-4](#).

All study visits (and visit windows), assessments, and procedures will be performed as indicated in the Schedule of Events ([Table 2-1](#)). On days when study drug is administered, assessments should be performed prior to dosing unless otherwise specified. Further details of study procedures and assessments can be found in the Study Reference and Laboratory Manuals.

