7.6.5.1 Efficacy Variables and Analysis (Phase 2)

Objective Response Rate (ORR) defined as the proportion of subjects with a best overall response of sCR, CR, VGPR, or PR, according to IMWG criteria ([Appendix A](#)) as assessed by the Investigator, will be used as the primary analysis for efficacy. The ORR along with a 95% CI, based on the Clopper-Pearson interval will be reported. Secondary analyses of ORR may be repeated in FAS, counting a missing best overall response as a non-responder. ORR will be summarized by each response assessment and best overall response.

Relative reduction in M-protein is defined as the maximum percent reduction from baseline in serum and urine M-protein levels at any time point while on treatment.

Progression-free survival (PFS) is defined as the time from first dose of study drug to first documentation of disease progression or death due to any cause. Subjects who do not experience PD and are alive will be censored at the time of last evaluable tumor assessment. Subjects who do not experience PD and start new anti-cancer therapy will be censored at the last evaluable tumor assessment on or prior to the time of the new anti-cancer therapy. For analyses conducted in the FAS, subjects with no evaluable post-baseline tumor assessments will be censored at the time of receipt of first study drug. Subjects who are lost to follow-up for assessment of PD will be censored at their last evaluable tumor assessment.

Overall Survival (OS) defined as the time from first dose of study drug until date of death due to any cause. Subjects without documentation of death at the time of analysis will be censored as of the date the subject was last known to be alive, or the data cut-off date, whichever is earlier.

PFS and OS will be summarized using Kaplan-Meier estimates.

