#### Precision

- Mean, Median, Q1, and Q3: one additional decimal place to that reported for Minimum and Maximum
- SD: two additional decimal places than the Minimum and Maximum
- Percentages: reported to one decimal place

Descriptive summaries will be presented by cohort and overall. No statistical significance test will be performed.

All data up to the time of study completion/withdrawal from the study will be included in the analysis, regardless of duration of treatment.

With exception to missing data handling noted in section 5.10, data will not be imputed for analysis purposes.

Summaries by visit will be produced for sample sizes  $\geq 2$ .

Numbering for data displays will be based on ICH E3.

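### SAP 5.5 sets no upper time limit on the maximum M-protein reduction, so values taken after a later anticancer therapy are not excluded

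*SAP*

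**What the plan says.** SAP 5.5 defines the measure: "Maximum percent reduction is defined as the largest percent reduction in the change from baseline at any visit". The same section fixes only the lower end of the window: "Post-baseline values will be those collected after the treatment start date". SAP 4 (under Precision) adds: "All data up to the time of study completion/withdrawal from the study will be included in the analysis, regardless of duration of treatment". SAP 7.2 summarises the maximum by cohort, while SAP 7.1 only lists investigator-assessed response.

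Protocol section 6 lists the endpoint in the same words for Phase 1 and Phase 2, with no time limit: "Relative reduction in serum and urine M-protein levels defined as the maximum percent reduction from baseline". Only protocol 7.6.5.1 says over what period the maximum is taken: "maximum percent reduction from baseline in serum and urine M-protein levels at any time point while on treatment". That section is headed Phase 2.

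The definition just before it in SAP 5.5, for most extreme change in CTCAE grade, does have a limit: "This calculation will consider assessments collected during the on-therapy period and assessed with CTCAE grading, scheduled or unscheduled". SAP 5.4 defines that period as running from treatment start to 28 days after the treatment end date.

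**The concern.** As written, the SAP's rule takes the largest fall seen at any time after the first dose. Under protocol 7.5, subjects who stop treatment for a reason other than progression "should continue tumor response assessments as per the standard of care frequency until disease progression is documented", or until consent is withdrawn or the study ends. Starting another anticancer therapy does not end these assessments, and protocol 7.4.7 lifts all treatment restrictions once the EOT visit is done. IMWG response rests largely on M-protein (protocol Appendix A), so such assessments would normally produce M-protein values. No SAP rule removes them.

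At stake is the one measure of clinical activity that the SAP summarises by cohort. A fall produced by the next therapy could enter a cohort's summary as if it had occurred on BION-1301.

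**Working it through.** **1. The windows side by side.**

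| Rule | Upper time limit | Cut at new therapy |
|---|---|---|
| SAP 5.5, maximum percent reduction | none | none |
| SAP 5.5, most extreme change (CTCAE grade) | treatment end date + 28 days | none stated |
| Protocol 6, M-protein endpoint (Phase 1 and Phase 2) | none | none |
| Protocol 7.6.5.1 (Phase 2), M-protein reduction | time on treatment | none stated |
| Protocol 7.6.5.1 (Phase 2), PFS | progression or death | yes, by censoring |

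The SAP had a bounded period available and used it for the neighbouring definition. The protocol also allowed for later therapy when it defined PFS.

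**2. When M-protein is measured.** Protocol Table 2-1 schedules SPEP/UPEP at screening, on Day 1 of the cycles and at EOT. Protocol 7.5 requires the EOT assessments to be completed before new therapy starts. Later scheduled follow-up is a call every 12 weeks about survival and subsequent therapy. Scheduled values are therefore protected. The open route is the continued response assessments quoted above, and it needs all of the following in one subject: treatment stopped without progression, a new therapy started, and M-protein then measured, recorded and used.

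**3. Direction.** The on-treatment values are a subset of the values at any visit. The maximum over the larger set is equal to or greater than the maximum over the subset. The error is zero or upward.

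**4. One subject (all values assumed).** Baseline serum M-protein 2.0 g/dL; on treatment 1.9 and 1.8; at EOT 2.1; after new therapy 0.8. Percent reduction = (baseline − value) / baseline × 100:
- 1.9 gives 5%; 1.8 gives 10%; 2.1 gives −5%
- 0.8 gives 60%

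The EOT value is 0.3 g/dL (0.3/1.8 = 16.7%) above the lowest value. That is below the serum progression thresholds in protocol Appendix A (25% and 0.5 g/dL), so this subject could be on the open route. The maximum is 10% through EOT and 60% at any visit, a rise of D = 50 points.

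**5. Effect on a cohort mean.** If one subject's maximum rises by D points, the mean rises by D/n. Actual cohort sizes are not given. The 3+3 design implies about 3 to 6, and SAP 3.1 reports 21 subjects in 6 cohorts (21/6 = 3.5 on average).

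| Assumed D | n = 3 | n = 6 | all 21 |
|---|---|---|---|
| 25 | 8.3 | 4.2 | 1.2 |
| 50 | 16.7 | 8.3 | 2.4 |
| 90 | 30.0 | 15.0 | 4.3 |

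These are illustrations, not estimates. The plan states no figure on this point to reproduce.

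**The case against.** The strongest reply is that the plan already prevents the problem. SAP 5.7 bases summaries on nominal visits, and the last nominal visit with M-protein is EOT, before new therapy. Unscheduled data may enter only some summaries, among them those of most extreme values. SAP 5.5 defines most extreme change as a CTCAE grade change, separately from maximum percent reduction. On that reading, later values would be listed but never enter the maximum. The SAP 4 sentence may be meant only to keep briefly treated subjects in the analysis. Protocol Appendix A requires confirming assessments before any new therapy. The endpoint is secondary and descriptive, with no test. Medians and quartiles are reported beside the mean, and the by-subject listings would show a late value.

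Most of this stands, and it narrows the exposure a great deal. It does not close it. Whether a maximum reduction counts as a most extreme value under SAP 5.7 is open to interpretation, so two programmers could produce different results. The Appendix A rule governs response categories, whereas the maximum can rest on a single value. A median is less sensitive than a mean, but with 3 subjects it can still move.

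A reader might also infer that the SAP contradicts the protocol and that SAP 10 should have declared the change. The documents do not support that. The limit to time on treatment stands in the Phase 2 analysis section, the SAP is confined to Phase 1, and the Phase 1 endpoint has no time limit in either document. What can be said is that the SAP departs from the only operational definition the protocol gives for an identically worded endpoint.

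**Conclusion.** The point holds as a gap in the definition. SAP 5.5 leaves the window for the maximum open at the upper end, and nothing in the SAP excludes values taken after a new anticancer therapy. If such values exist and are used, the error can only favour BION-1301, in the only activity measure summarised by cohort. For one affected subject, with an assumed rise of 25 to 90 points, the cohort mean would shift by 8.3 to 30.0 points at n = 3 and 4.2 to 15.0 points at n = 6.

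It would go too far to conclude that another therapy's effect will be credited to BION-1301. The documents do not say how many subjects stopped without progression, started another therapy and had later M-protein recorded, and the number may be zero. No hypothesis test or sample-size figure is affected.

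**What to change.** In SAP 5.5, restrict maximum percent reduction to post-baseline values that fall in the on-therapy period of SAP 5.4 (treatment start to treatment end date + 28 days), including the EOT visit assessment, and before the start of any new anticancer therapy. Later values are listed only. EOT needs to be named because its window runs to 28 + 7 = 35 days after the last dose, which can be up to 7 days past the on-therapy period.

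The cost is one sentence and one date filter. The filter needs the start date of new therapy. Protocol 7.5 and 7.5.2.3 say that subsequent therapies are recorded but do not mention start dates, so this should be checked in the database. The window is somewhat wider than a literal reading of time on treatment. The downside is that a late reduction without new therapy, after the window closes, would be listed but not summarised.
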